7.2.7. No Evidence of Response (NR)

For subjects to be classified as being in NR, they must have at least one evaluable bone marrow aspirate or biopsy and not meet the criteria for PR or better. For subjects who do not have evaluable bone marrow aspirate or biopsy, but have presence of leukemic blasts in the peripheral blood, the response is considered as NR.

7.3. Overall Survival (OS)

Overall survival is the time from randomization until death from any cause.

7.4. Event-Free Survival (EFS)

Event-free survival is the time from randomization until documented refractory disease, relapse after CRc, or death from any cause, whichever is observed first.

7.5. Leukemia-Free Survival (LFS)

Leukemia-free survival is the time from the first documented response (CR, CRp, CRi) until documented relapse or death from any cause.

7.6. Composite Complete Remission (CRc) Rate

Composite complete remission (CRc) rate is the percentage of subjects achieving a best response of CR, CRp, or CRi.

7.7. Complete Remission (CR) Rate

Complete remission (CR) rate is the percentage of subjects achieving CR.

7.8. Duration of CRc

Duration of CRc is the time from the first documented CRc (CR+CRp+CRi) until documented relapse.

7.9. Duration of CR

Duration of CR is the time from the first documented complete remission (CR) until documented relapse.

7.10. Transplantation Rate

Transplantation rate is the percentage of subjects undergoing HSCT directly following protocol specified treatment with no intervening AML therapy.

8. SAFETY EVALUATION

All subjects receiving at least 1 dose of quizartinib or salvage chemotherapy will be evaluable for safety and defined as the Safety Analysis Set. Safety will be assessed with physical examinations, vital sign determinations, 12-lead ECGs, AE evaluations, and clinical laboratory tests (hematology, serum chemistry, and urinalysis results). The safety data will also be summarized for pre-defined sub-groups.

Study drug toxicity will be assessed continuously. AEs will be evaluated during the study according to NCI CTCAE v4.03 until 30 days after the last dose of study treatment.

Subjects should be instructed to report any new AE or worsening of an existing AE immediately.

8.1. Medical History

Each subject's medical history must be obtained at screening. Information on any prior or existing medical conditions and/or surgical procedures will be recorded on the appropriate CRF.

8.2. Physical Examination

A complete physical examination will be performed at screening to establish a baseline for study entry, and at additional times specified in the study schedule (Section 5.8). Whenever possible, the same individual will perform subsequent examinations to identify changes from baseline. Symptom-directed physical examinations performed during the treatment period will be based on the subject's medical history and AEs, and will include weight determination and a review of body systems.

8.3. Vital Signs

Vital signs, including systolic and diastolic blood pressures, pulse rate, respiratory rate, and body temperature will be determined and recorded at the times specified in the study schedule (Section 5.8). All vital sign measurements should be obtained with subject's supine for at least 5 minutes before determination. Whenever multiple assessments are scheduled at the same time, they should occur in the order of ECGs, vital sign determinations, and blood sample collection.

8.4. Electrocardiograms

Supine triplicate 12-lead ECGs will be obtained at the times specified in the study schedule (Section 5.8). Additional ECGs may be obtained at the Investigator's discretion. Subjects undergoing dose escalation due to lack of response or loss of response after cycle 2 day 1 should be monitored carefully for QT prolongation which should include at least weekly ECGs for 2 weeks.

Electrocardiograms will be recorded in triplicate (3 separate ECGs at least 3 minutes apart but preferably no more than 5 minutes apart; the average of the 3 QTcF determinations will be used to determine safety parameters and dose escalation at Day 16 day of quizartinib administration) and transmitted electronically to a central ECG laboratory. Electrocardiograms will be reviewed by a suitably-qualified physician at the study site to allow immediate decisions about subject safety. When an ECG abnormality of concern is suspected (eg, QTcF >480 msec), the site will

contact the central ECG laboratory to obtain an expedited (within 24 hours) evaluation, and the site will use the central laboratory's analysis for decisions on changes in subject care and protocol compliance. The ECG should be repeated in triplicate within 2 hours on the same day for analysis by the central laboratory. Results of the central ECG laboratory analysis will be the final data for the ECG database. Electrocardiograms will be submitted to the FDA ECG warehouse, if required by the FDA. QTcF duration will be used to make all decisions based on QT criteria.

Guidelines for ECG monitoring are as follows:

- Electrocardiograms will be obtained after the subject has rested quietly and is awake and fully supine for 10 minutes before the first of the triplicate ECGs.
- Additional ECGs can be obtained at any time if clinically indicated. It is important to record actual clock time for each assessment. The triplicate ECGs will be recorded and the average QTcF interval will be determined for each time point.

If clinically significant ECG changes from baseline at screening are noted, the changes will be recorded as AEs on the appropriate CRF. Clinically significant changes will be defined as any ECG variations that are medically significant and could cause a change in medical care. The Investigator must continue to monitor the subject until any ECG changes return to normal.

8.5. Management of QT Prolongation

Quizartinib is known to be associated with prolongation of the QT interval. To reduce the risk of cardiac arrhythmias, it is important to maintain serum electrolytes (K^+ , Ca^{++} , and Mg^{++}) within normal range and ideally maintain K^+ above 4.0 mEq/L. Subjects in the quizartinib arm who experience QTcF prolongation \geq Grade 2 should be managed according to the guidelines below.

- Grade 2 (QTcF average of triplicate readings > 480 msec)
 - Electrolytes (potassium, calcium and magnesium) should be checked and supplementation given to correct any values outside the normal range
 - Concomitant medications should be reviewed to identify and, if appropriate, discontinue any medication with known QT prolonging effects
 - The dose of quizartinib will be reduced one level without interruption of dosing
 - Quizartinib dose may be re-escalated after 1 cycle at reduced dose if QT prolongation has decreased to \leq Grade 1 but subject must be monitored closely for QT prolongation for first cycle at the increased dose.
- Grade 3 (QTcF average of triplicate readings > 500 msec)
 - Electrolytes (potassium, calcium and magnesium) should be checked and supplementation given to correct any values outside the normal range
 - Concomitant medications should be reviewed to identify and, if appropriate, discontinue any medication with known QT prolonging effects
 - Quizartinib dosing will be interrupted for up to 14 days. If QTcF returns to within 30 msec of baseline or ≤ 450 msec within 14 days, treatment may be resumed at a

reduced dose. Quizartinib dose cannot be escalated following dose reduction for Grade 3 QTcF prolongation.

- Grade 4 (QTcF average of triplicate readings >500 msec or >60 msec change from baseline, and Torsade de pointes or polymorphic ventricular tachycardia or signs/symptoms of serious arrhythmia)
 - Electrolytes (potassium, calcium and magnesium) should be checked and supplementation given to correct any values outside the normal range
 - Concomitant medications should be reviewed to identify and, if appropriate, discontinue any medication with known QT prolonging effects
 - Quizartinib dosing will be permanently discontinued.

Subjects who experience Grade 2 or higher QTcF prolongation and undergo dose interruption and/or reduction must be monitored closely with repeat ECGs to ensure resolution of the QTcF prolongation. QTcF prolongation \geq Grade 3, either serious or non-serious and whether or not causally related, must be recorded as AE or SAE and reported on a SAE reporting form within 24 hours of awareness, with the investigator's assessment of seriousness, causality, and a detailed narrative.

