If any of the following criteria are met, the quizartinib dose will be reduced stepwise from 60 mg/day to 30 mg/day or from 30 mg/day to 20 mg/day or discontinued. No further dose reductions below 20 mg/day will be allowed.

- **QTcF prolongation**

- Grade 2 (QTcF average of triplicate readings > 480 msec) (All toxicity grades according to National Cancer Institute Common Terminology Criteria for Adverse Events [NCI CTCAE] v4.03)
 - The dose will be reduced without interruption.
 - If 20 mg/day is the current dose, dosing will be interrupted for up to 14 days. If QTcF returns to within 30 msec of baseline or ≤ 450 msec within 14 days, treatment may be resumed at 20 mg/day.
- Grade 3 (QTcF average of triplicate readings > 500 msec)
 - Dosing will be interrupted for up to 14 days. If QTcF returns to within 30 msec of baseline or ≤ 450 msec within 14 days, treatment may be resumed at a reduced dose.
 - If 20 mg/day is the current dose, dosing will be interrupted for up to 14 days. If QTcF returns to within 30 msec of baseline or ≤ 450 msec within 14 days, treatment may be resumed at 20 mg/day. If Grade 3 event returns, treatment will be discontinued.
- Grade 4 (QTcF > 500 msec or > 60 msec change from baseline, and Torsade de pointes or polymorphic ventricular tachycardia or signs/symptoms of serious arrhythmia)
 - Treatment will be discontinued.

- **Non-hematologic toxicity**

- Grade 3 or 4 related to quizartinib and persisting >48 hours without improvement to \leq Grade 2
 - Dosing will be interrupted for up to 14 days.
 - If toxicity improves to \leq Grade 1 within 14 days, treatment may be resumed at the reduced dose.

- **Myelosuppression**

- In a subject with CRp or CRi, the dose may be reduced at the Investigator's discretion if:
 - The subject has been treated for a minimum of 2 cycles.
 - Platelet count is $<100 \times 10^9/L$ and absolute neutrophil count (ANC) is $\leq 1000 \times 10^9/L$.

- Marrow blasts < 5%.
- There is no evidence of extramedullary disease.
- **Initiation of concomitant treatment with a strong CYP3A4 inhibitor**
 - The dose will be reduced from either 60 mg/day to 30 mg/day or from 30 mg/day to 20 mg/day.
 - A subject taking a strong CYP3A4 inhibitor at time of randomization will initiate quizartinib administration at 20 mg/day.

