5.1.2. Treatment

A flow chart of study activities is presented in [Figure 1](#).

For subjects randomized to quizartinib the starting dose will be 30 mg/day unless the subject is receiving concurrent therapy with a strong CYP3A4 inhibitor, in which case the starting dose will be 20 mg/day. The dose will be taken in the morning with or without food over continuous 28-day cycles. If the subject omits taking quizartinib in the morning, it may be taken later in the day (until midnight), otherwise the dose should be considered missed. If the subject vomits after

taking quizartinib, no replacement dose should be given. Detailed information on quizartinib dosing is provided in Section 5.6.4.1.

The dose of quizartinib will be increased at Day 16 or Cycle 2 Day 1 according to the criteria specified in Section 5.6.4.3. Following dose escalation, triplicate ECG determinations should be performed at least once weekly for 2 weeks to monitor QTcF prolongation.

If necessary, the dose of quizartinib may be reduced according to the criteria described in Section 5.6.4.4.

See also Section 8.5 for details of QTcF management when prolongation is observed.

[figure not shown]
In subjects receiving quizartinib or LoDAC, treatment should continue until there is no longer clinical benefit from therapy, or until unacceptable toxicity occurs. For subjects receiving LoDAC the initiation of cycles may be delayed for up to 14 days to allow for recovery from toxicity.

Subjects that receive either quizartinib or LoDAC will be assessed for response on Day 1 of Cycle 2 and Day 1 of Cycle 3 as well as on Day 1 of each subsequent cycle unless the subject has already achieved CR, CRp, or CRi. In that event, bone marrow testing will be repeated after every 3 subsequent cycles, unless there is evidence of relapse.

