5.6. Study Treatment

5.6.1. Identity of Investigational Product

The investigational medicinal product is supplied to the pharmacy as quizartinib 30 mg yellow tablets (26.5 mg free base) or 20 mg white tablets (17.7 mg free base) of AC010220•2HCl. All packages are shipped at conditions depicted on the product label.

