5.6.4.4. Quizartinib Dose Reduction Rules and Definitions

The dose of quizartinib will be reduced stepwise from 60 mg/day to 30 mg/day or from 30 mg/day to 20 mg/day, based on the following criteria:

QTcF (QT interval corrected with Fridericia's formula) Prolongation

- Grade 2 (QTcF average of triplicate readings > 480 msec)
 - The dose will be reduced without interruption.
 - If 20 mg/day is the current dose, dosing will be interrupted for up to 14 days. If QTcF returns to within 30 msec of baseline or ≤ 450 msec within 14 days, treatment may be resumed at 20 mg/day.
- Grade 3 (QTcF average of triplicate readings > 500 msec)
 - Dosing will be interrupted for up to 14 days. If QTcF returns to within 30 msec of baseline or ≤ 450 msec within 14 days, treatment may be resumed at a reduced dose.
 - If 20 mg/day is the current dose, dosing will be interrupted for up to 14 days. If QTcF returns to within 30 msec of baseline or ≤ 450 msec within 14 days, treatment may be resumed at 20 mg/day. If Grade 3 event returns, treatment will be discontinued.
- Grade 4 (QTcF >500 msec or >60 msec change from baseline, and Torsade de pointes or polymorphic ventricular tachycardia or signs/symptoms of serious arrhythmia)
 - Treatment will be discontinued.

See Section 8.5 for clinical guidelines for the management of QT prolongation.

Non-hematologic Toxicity

Grade 3 or 4 related to quizartinib and persisting >48 hours without improvement to \leq Grade 2.

- Dosing will be interrupted for up to 14 days.

- If toxicity improves to \leq Grade 1 within 14 days, treatment may be resumed at the reduced dose.

Myelosuppression

In a subject with CRp or CRi, the dose may be reduced at the Investigator's discretion if:

- The subject has been treated for a minimum of 2 cycles.
- Platelet count is $<100 \times 10^9/L$ and ANC is $\leq 1000 \times 10^9/L$.
- Marrow blast count is $<5\%$.
- There is no evidence of extramedullary disease.

Initiation of concomitant treatment with a strong CYP3A4 inhibitor is identified in [Appendix 1: List of Potential QT Prolonging Drugs, CYP3A4 Inhibitors/Inducers, and P-glycoprotein Inhibitors/Inducers](#).

The dose will be reduced one level (60 mg to 30 mg or 30 mg to 20 mg) when treatment with a strong CYP3A4 inhibitor is initiated.

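### Section 8.5 omits the 20 mg/day exception for Grade 2 QTcF prolongation, so at that dose its rule cannot be carried out and conflicts with Section 5.6.4.4 and the synopsis

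*Combined protocol and SAP*

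**What the plan says.** Section 8.5 applies to every quizartinib-arm subject with QTcF prolongation of Grade 2 or higher. Besides electrolyte and co-medication checks, its dosing instruction for Grade 2 is: "The dose of quizartinib will be reduced one level without interruption of dosing". The current dose is not mentioned.

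Section 5.6.4.4 starts from the same general rule for Grade 2 and then adds an exception: "If 20 mg/day is the current dose, dosing will be interrupted for up to 14 days". Treatment may restart at 20 mg/day if, within those 14 days, QTcF comes back to no more than 30 msec from baseline or to 450 msec or lower. The synopsis (Study Treatment) carries the same exception and sets the floor: "No further dose reductions below 20 mg/day will be allowed". Section 5.6.1 is consistent with that floor: the drug is "supplied to the pharmacy as quizartinib 30 mg yellow tablets" or as 20 mg tablets.

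On which section to use:

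- Section 5.1.2 sends the reader to 5.6.4.4 for dose-reduction criteria and then adds: "See also Section 8.5 for details of QTcF management when prolongation is observed".
- Section 5.6.4.1 also names 5.6.4.4 for dose reduction.
- Section 5.6.4.4 itself says: "See Section 8.5 for clinical guidelines for the management of QT prolongation".
- Section 8.5 contains no reference back to 5.6.4.4.

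**The concern.** Section 8.5 is the protocol's dedicated text on QT prolongation, a known risk of the drug, and two other sections direct sites to it. For a subject on 20 mg/day with Grade 2 prolongation, it orders a step down to a dose that does not exist. The only half of the sentence that can still be obeyed is the half that says not to interrupt. Obeying it leaves the subject on drug with QTcF above 480 msec, when Section 5.6.4.4 and the synopsis require dosing to stop.

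The situation is reachable. Under Sections 5.2.4 and 5.6.4.1, 20 mg/day is the planned starting dose for anyone taking a strong CYP3A4 inhibitor. It is also where a subject lands after a reduction from 30 mg. What is at stake is subject safety and consistent handling across about 150 centers, not the statistical inference.

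**Working it through.** No figure in the plan needs reproducing. The check sets the three Grade 2 rules side by side at each permitted dose. The inputs are the Grade 2 bullets of Section 8.5, Section 5.6.4.4 and the synopsis, the 60-30-20 mg/day ladder (5.6.4.4 and synopsis), and the 20 mg floor (synopsis).

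| Current dose | Section 8.5 | Section 5.6.4.4 | Synopsis | Consistent? |
|---|---|---|---|---|
| 60 mg/day | 30 mg, no interruption | 30 mg, no interruption | 30 mg, no interruption | Yes |
| 30 mg/day | 20 mg, no interruption | 20 mg, no interruption | 20 mg, no interruption | Yes |
| 20 mg/day | One level lower, no interruption; no such level | Interrupt for up to 14 days; may resume 20 mg on recovery | As 5.6.4.4 | No |

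The last row differs in two ways. First, the reduction in 8.5 cannot be made. Second, the interruption that 8.5 rules out is the one the other two texts require. Per subject, that is 0 days off drug under the executable half of 8.5, against up to 14 days under 5.6.4.4. Since 5.6.4.4 and the synopsis agree with each other and with the floor, the defect lies in 8.5.

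The same comparison for Grade 3 at 20 mg/day:

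- Section 8.5 stops the drug: "Quizartinib dosing will be interrupted for up to 14 days". It then allows a restart only at a reduced dose, and there is none below 20 mg. Read literally, treatment does not restart.
- Section 5.6.4.4 and the synopsis also interrupt, but allow a restart at 20 mg on recovery and add: "If Grade 3 event returns, treatment will be discontinued".

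Here 8.5 is incomplete, but on the cautious side.

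The number of subjects affected cannot be worked out. The documents do not give the share expected to be on 20 mg/day or a QTcF event rate at that dose. The lowest doses in Table 2 are 30 mg (Grade 2 in 5%) and 60 mg (14%), and carrying those rates over to 20 mg, often with a strong inhibitor on board, would be guesswork.

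**The case against.** The best defence is that the correct rule already sits where the protocol tells sites to look. Sections 5.1.2 and 5.6.4.1 both name 5.6.4.4 for dose-reduction criteria, and 8.5 is introduced only as a further reference or as clinical guidelines. Section 8.5 also reads more like a shortened restatement than a rival rule: it repeats the general line of 5.6.4.4 and drops the exception. It does not define its dose levels, so a site needs the ladder in 5.6.4.4 or the synopsis, where the 20 mg rule also appears. An order that plainly cannot be followed may well prompt a check. Other protections remain: expedited central ECG reading and a same-day repeat above 480 msec (8.4), electrolyte and co-medication review (8.5), and withdrawal of study treatment on the investigator's judgment (5.4.5).

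Most of this stands, and it limits the weight of the point. It does not remove it. No text says that 5.6.4.4 prevails, 8.5 applies without exception to every Grade 2 case, and nothing in 8.5 leads back to the full rule. One safeguard is also weaker than it looks. The close repeat ECGs at the end of 8.5 are required for subjects who have Grade 2 or higher prolongation and whose dosing is interrupted or reduced. A subject simply kept on 20 mg has had neither.

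A reader might infer that the protocol as a whole directs continued dosing at 20 mg. The documents do not support that: two of the three texts require interruption, and one of them is the named source of the criteria. Harm requires a site to rely on 8.5 alone and to act on only half of its sentence.

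**Conclusion.** The conflict is real and narrow: one dose level, one grade, one section. It rests on the wording alone and needs no numerical assumption. The consequence is possible continued dosing at 20 mg/day with QTcF above 480 msec, and it assumes a site works from 8.5 without consulting 5.6.4.4 or the synopsis. The count of such subjects cannot be derived. Sample size, alpha, power and the OS analysis are unaffected. It should be corrected because the risk is cardiac and the correction is nearly free.

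Two wider readings should not be drawn. A reader might infer that the Grade 3 bullet of 8.5 is also unsafe at 20 mg; it is not, because it stops the drug, and its gap concerns only whether and how treatment restarts. A reader might also infer that 8.5 and 5.6.4.4 contradict each other on re-escalation after a Grade 2 reduction. They do not: 8.5 adds conditions that 5.6.4.4 omits, both can be followed together, and 5.6.4.4 refers to 8.5.

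**What to change.** In Section 8.5:

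1. Grade 2 bullet: add the 20 mg/day branch from 5.6.4.4. Interrupt for up to 14 days; resume at 20 mg if QTcF returns to within 30 msec of the baseline value or falls to 450 msec or less.
2. Grade 3 bullet: allow resumption at 20 mg on the same recovery criterion, with discontinuation if Grade 3 recurs.
3. Add a cross-reference stating that 5.6.4.4 governs dose changes for QTcF prolongation.

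The cost is protocol wording and a clarification to sites. The rules already exist in 5.6.4.4 and the synopsis, so no new assessment, dose level or tablet strength is needed, and the statistical plan does not change.

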8.6. Clinical Laboratory Evaluations

Serum chemistry, urinalysis and hematology tests will be performed at the time specified in the study schedule (Section 5.8). A central laboratory will perform all tests unless this is not feasible, in which case a local laboratory may be used.

The determinations identified in [Table 8](#) will be done.

Table 8 Clinical Laboratory Determinations

Hematology			
Hematocrit	Hemoglobin	Mean corpuscular hemoglobin	Mean corpuscular hemoglobin concentration
Mean corpuscular volume	Platelets	Red Blood Cells	White blood cells (total)
White blood cell differential (% and absolute count)			
Clinical Chemistry			
Albumin	Alanine transaminase	Alkaline phosphatase	Aspartate transaminase
Bicarbonate	Bilirubin, direct	Bilirubin, total	Blood urea nitrogen
Calcium	Chloride	Cholesterol*	Creatine phosphokinase
Creatinine	Gamma-glutamyl transaminase	Glucose	High density lipoprotein*
Lactate dehydrogenase	Lipase	Low density lipoprotein*	Magnesium
Phosphorus	Potassium	Sodium	Total protein
Triglyceride*		Uric acid	
Urinalysis			
Appearance	Bilirubin	Blood	Color
Glucose	Ketones	pH	Protein
Specific Gravity			

*At screening and end of treatment only. Fasting is not required.

